**Appendix 6 SLEDAI-2K: DATA COLLECTION SHEET**

Enter weight in SLEDAI-2K score column if descriptor is present at the time of the visit or in the **preceding 10 days**.

Note that Leukopenia will not be evaluated for reasons of functional blinding [see Section [5.1.4.2](#)] and CH50 will not be assessed by central laboratory.

Hematuria, proteinuria and pyuria are evaluated by dipstick at each visit assessing SLEDAI-2K. If the dipstick results are positive, urine sample will be further analyzed as clinically indicated (i.e., microscopic analysis of WBC, RBC, casts, and protein quantification).

## Appendix 7 Notable abnormalities for ECG, BP and laboratory variables

### Notable abnormalities for ECG and BP

Notable abnormalities for ECG and BP that are related to the potential effects of ACT-334441 will address the following variables:

- Morphological ECG findings (defined as any abnormal finding not present prior to start of treatment)
- HR outliers (bpm), based on ECG
- PR interval (ms)
- QT/QTc interval (ms), based on Bazett's or Fridericia's formula
- BP (mmHg)

The definition of the abnormal values to be reported will be described in the SAP.

### Laboratory abnormalities

Laboratory values below or above the normal range will be graded at three levels (H, HH, HHH for values above normal range and L, LL, LLL for values below the normal range) where L stands for "low", H for "high".

The term "marked abnormality" describes laboratory values above or below the thresholds, with grading of abnormalities at two levels: LL/HH and LLL/HHH. These thresholds have been defined by the sponsor in order to flag and/or communicate abnormal laboratory results from the central laboratory to the investigators, and for the purpose of standardized data analysis and reporting by the sponsor. The definitions of marked abnormal values are based mainly on the Common Terminology Criteria for Adverse Events (CTCAE) grading system (2010 v4.03) and, in specific cases (e.g., lymphocyte levels), are adjusted based on the known PD effect of the study drugs (e.g., LLL threshold for lymphocytes) [CTCAE 2010].

The term ALERT here corresponds to protocol-defined test result threshold requiring an action from the investigator as described in the protocol (e.g., repeat the test; interrupt or discontinue the study drug) and should not be confused with the term "call alert" used by the central laboratory for laboratory results, which will be communicated to the investigator. Not all ALERTS listed in this table will be "call alerts" from the central laboratory and vice versa.

PLEASE NOTE: Thresholds for abnormality of level L or H are not provided in this appendix but will be provided in the laboratory manual. Parameters for which no threshold is defined in [Table 5](#) below may be defined in the central laboratory manual.

**Table 5**      **Thresholds for marked laboratory abnormalities for ACT-334441**

Parameter	LL	LLL	HH	HHH
Hemoglobin	< 100 g/L (< 10g/dL; < 6.2 mmol/L)	< 80 g/L (<8g/dL; < 4.9 mmol/L)	Increase in > 20 g/L above ULN or above baseline (if baseline is above ULN)	Increase in > 40 g/L above ULN or above baseline (if baseline is above ULN)
MCH	ND	ND	ND	ND
MCV	ND	ND	ND	ND
MCHC	ND	ND	ND	ND
Hematocrit	< 28% (female) < 32% (male)	< 20%	> 60% (male) > 55% (female)	> 65%
Platelet count	< 75 × 10 e9 /L (< 75,000/mm  )	< 50.0 × 10 e9 /L (<50,000/mm  )	> 600 × 10 e9 /L	> 999 × 10 e9 /L
RBC count	ND	ND	ND	ND
WBC count	ND	< 1.9 × 10 e9 /L	> 20.0 × 10 e9 /L (>20 000/mm  )	CTCAE (grade 3) > 100.0 × 10 e9 /L (>100 000/mm  )
Lymphocyte	ND	< 0.2 × 10 e9 /L (< 200/mm  ) ALERT* < 0.2 × 10 e9 /L (< 200/mm  )	> 4.0 × 10 e9 /L (> 4000/mm  )	≥ 8 × 10 e9 /L (> 8000/mm  )
Neutrophils	< 1.5 × 10 e9 /L (< 1,500/mm  )	< 1.0 × 10 e9 /L (< 1000/mm  )	ND	ND
Eosinophils	ND	ND	> 5.0 × 10 e9 /L or > 5% (> 5000 cells/mm  )	ND
Monocytes	ND	ND	ND	ND
Basophils	ND	ND	ND	ND
Polymorphonuclear leucocyte/Band cells	ND	ND	> 90%	> 95%
AST	ND	ND	≥ 3 ULN (U/L) ALERT ≥ 3 ULN	≥ 5 ULN (U/L) ALERT ≥ 5 ULN ≥ 8 ULN
ALT	ND	ND	≥ 3 ULN (U/L) ALERT ≥ 3 ULN	≥ 5 ULN (U/L) ALERT ≥ 5 ULN ≥ 8 ULN
Total bilirubin	ND	ND	≥ 2 ULN (umol/L) ALERT ≥ 2 ULN combined with ALT or AST ≥ 3 ULN	≥ 5 ULN (umol/L)
Alkaline Phosphatase	ND	ND	> 2.5 ULN (U/L)	> 5 ULN (U/L)

Confidential

INR	ND	ND	≥ 1.5 ULN** or ≥ 1.5 times above baseline if on anticoagulation ALERT ≥ 1.5 combined with ALT or AST ≥ 3 ULN	≥ 2.5 ULN** or ≥ 2.5 times above baseline if on anticoagulation
Activated partial thromboplastin time prolonged (aPTT)	ND	ND	> 1.5 - 2.5 × ULN	> 2.5 × ULN
Lactate dehydrogenase	ND	ND	ND	ND
Creatinine	ND	ND	> 1.5 ULN (umol/L) or > 1.5 × baseline	> 3 ULN (umol/L) or > 3 × baseline
Creatinine Clearance (eGFR)	<60 ml/min/1.73m 	<30 ml/min/1.73m 	ND	ND
Urea	ND	ND	> 2.5 ULN (mmol/L)	> 5 ULN (mmol/L)
Uric acid	ND	ND	> 0.59 mmol/L (>10 mg/dL)	> 0.72 mmol/L (>12 mg/dL)
Proteinuria	ND	ND	≥1.0 g/24h	≥3.5 g/24h
Protein/creatinine ratio	ND	ND	>100 mg/mmol***	>300 mg/mmol***
Albumin	< 30 (g/L)	< 20 (g/L)	ND	ND
Protein total	ND	ND	ND	ND
C-reactive protein	ND	ND	ND	ND
Glucose (Non-diabetic Fasting)	< 3.0 (mmol/L) (< 55 mg/dL)	< 2.2 (mmol/L) (< 40 mg/dL)	> 8.9 (mmol/L) (> 160 mg/dL)	> 13.9 (mmol/L) (> 250 mg/dL)
Potassium	< 3.2 (mmol/L)	< 3.0 (mmol/L)	> 5.5 (mmol/L)	> 6.0 (mmol/L)
Sodium	ND	< 130 (mmol/L) (< 130 mEq/L)	> 150 (mmol/L) (> 150 mEq/L)	> 155 (mmol/L) (> 155 mEq/L)
Calcium (corrected for albumin)	< 2.0 (mmol/L) (< 8.0 mg/dL)	< 1.75 (mmol/L) (< 7.0 mg/dL)	> 2.9 (mmol/L) (> 11.5 mg/dL)	> 3.1 (mmol/L) (> 15.5 mg/dL)
Chloride	ND	ND	ND	ND
Triglyceride	ND	ND	> 3.42 (mmol/L)	> 11.4 (mmol/L)
Cholesterol	ND	ND	> 7.75 (mmol/L)	> 12.92 (mmol/L)
Fibrinogen	< 0.75 - 0.5 LLN or 25 - < 50% decrease from baseline	< 0.25 LLN or < 75% decrease from baseline or absolute value < 50 mg/dL	ND	ND
IgG	ND	ND	ND	ND
IgM	ND	ND	ND	ND
IgA	ND	ND	ND	ND

ANA	ND	ND	ND	ND
Anti-dsDNA	ND	ND	ND	ND
C3	ND	ND	ND	ND
C4	ND	ND	ND	ND
Anti-Sm	ND	ND	ND	ND
Antiribosomal P	ND	ND	ND	ND
Anti-cardiolipin IgA	ND	ND	ND	ND
Anti-cardiolipin IgG	ND	ND	ND	ND
Anti-cardiolipin IgM	ND	ND	ND	ND
Serum pregnancy test	ND	ND	ND	Positive ALERT: Positive

ALT = alanine aminotransferase; ANA = anti-nuclear antibodies; anti-dsDNA = anti-double-stranded DNA; anti-Sm = anti-Smith; aPTT = activated partial thromboplastin time; AST = aspartate aminotransferase; CTCAE = Common Terminology Criteria for Adverse Events; eGFR = estimated glomerular filtration rate; INR = international normalized ratio; MCH = mean corpuscular hemoglobin; MCHC = Mean corpuscular hemoglobin concentration; MCV = mean corpuscular volume; ND = not defined; RBC = red blood cell; ULN = upper limit of normal; WBC = white blood cell.

\*If lymphocyte count < 800 cells/ $\mu$ l at EOS visit, an alert will be sent.\*\* HH and HHH based on CTCAE 2010 v4.03 [CTCAE 2010]. However, an Alert will be sent when INR  $\geq$  1.5 based on the guidance for monitoring liver test abnormalities from Food and Drug Administration (FDA) [FDA 2009]. \*\*\*Source for protein/creatinine ratio thresholds: <http://www.renal.org/information-resources/the-uk-eckd-guide/proteinuria#sthash.jdT5cPIP.dpbs>.

[figure not shown]

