### ANA, anti-dsDNA, complement factors and exploratory biomarkers

ANA and anti-dsDNA are a hallmark of SLE, and titers of these autoantibodies have been found to correlate with clinical disease activity and the response to therapy [[Ravirajan 2001](#)]. Low C3 and C4 complement have also been found to correlate with clinical disease activity [[Swaak 1986](#)]. Immunoglobulins may be elevated in SLE patients, and cytokines and other soluble factors have been found to be elevated in serum of SLE patients.

The following biomarkers as indicated below (but not limited to) will be measured at baseline and during the course of study treatment in order to support the SLE diagnosis of involved subjects, to explore their predictive value for treatment response and to explore changes in response to ACT-334441 treatment.

- ANA, anti-dsDNA, complement C3 and C4 (all visits except Visit 3)
- IgM, IgG, IgA, CRP, fibrinogen, and BLYS (Visit 2 and Visits 4 to 7)
- anti-Smith, anti-cardiolipin (IgA, IgG, IgM) , anti-ribosomal P, (Visit 2 only).
- CXCL10 (EDTA-plasma; Visit 2 and Visits 4 to 7)

At Visit 1 (Screening), ANA and/or anti-dsDNA antibody testing should be positive in order to fulfill inclusion criterion 6 [see Section 4.3] unless a documented historical positive testing is available to confirm the subject's eligibility [see Section 4.6.2].

Aliquots of the EDTA plasma samples will be transferred to the sponsor for exploratory analysis of new soluble biomarkers potentially related to SLE and/or S1P1 modulation. Frozen samples will be kept for a maximum duration of 15 years and will be destroyed thereafter.

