For the parameters assayed as a categorical variable (e.g., Protein), the analysis value is defined only as a character value.

**Analysis Reference Range Indicator** is derived to identify marked abnormalities according the Adapted table 5 from the study protocol [included in Section 15]. It is only defined for results coming from the central laboratory, it is based on the normal range indicator provided by ACM (L, LL, H, HH) and augmented or modified according to the adapted table 5.

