| CHEMISTRY   | URATE     | Urate                                 | umol/L                     | M   | NA     | NA    | 262  | 452  | > 590                                | > 720                            |
| COAGULATION | APTT      | Activated Partial Thromboplastin Time | sec                        |     | NA     | 14.0  | 24   | 37   | > 1.5 - 2.5 $\times$ ULN             | > 2.5 $\times$ ULN               |

| Category    | Test Code | Test Name                          | Standard Unit | Se x | LLL  | LL  | LO     | HI     | HH   | HHH  |
|-------------|-----------|------------------------------------|---------------|------|--|---|--------|--------|--|--|
| COAGULATION | FIBRINO   | Fibrinogen                         | g/L           |      | < 0.25 LLN or < 75% decrease from baseline or absolute value < 0.5 | < 0.75 - 0.5 LLN or 25 - < 50% decrease from baseline | 2.1    | 4.7    | 6.0  | NA   |
| COAGULATION | INR       | Prothrombin Intl. Normalized Ratio | Fraction of 1 |      | NA   | NA  | 0.8    | 1 2    | $\geq 1.5$ ULN   | $\geq 2.5$ ULN   |
| COAGULATION | PT        | Prothrombin Time                   | sec           |      | NA   | NA  | 9.4    | 13     | NA   | 100.1  |
| HEMATOLOGY  | EOS       | Eosinophils                        | 10e9/L        |      | NA   | NA  | 0      | 0 5    | > 5.0  | ND   |
| HEMATOLOGY  | HCT       | Hematocrit                         | L/L           | F    | < 20   | < 28  | 0.36 4 | 0.48 9 | > 55   | > 65   |
| HEMATOLOGY  | HCT       | Hematocrit                         | L/L           | M    | < 20   | < 32  | 0.41 6 | 0 54 1 | > 60   | > 65   |
| HEMATOLOGY  | HGB       | Hemoglobin                         | g/L           | F    | < 80 g/L   | < 100 g/L   | 115    | 160    | Increases in > 20 g/L above ULN or Increases in > 20 g/L above baseline (if baseline is above ULN) | Increases in > 40 g/L above ULN or Increases in >40g/L above baseline (if baseline is above ULN) |

| Category   | Test Code | Test Name          | Standard Unit | Sex | LLL    | LL    | LO   | HI   | HH   | HHH   |
|------------|-----------|--------------------|---------------|-----|--------|-------|------|------|--|---|
| HEMATOLOGY | HGB       | Hemoglobin         | g/L           | M   | < 80   | < 100 | 130  | 175  | Increases in > 20 g/L above ULN or Increases in > 20 g/L above baseline (if baseline is above ULN) | Increases in > 40 g/L above ULN or Increases in > above baseline (if baseline is above ULN) |

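### The fibrinogen LLL criterion runs the wrong way: small falls from baseline meet the gravest low grade, falls of 75% or more do not, and values of 0.25-0.5 LLN miss both marked grades by level

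*Protocol*

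**What the plan says.** Protocol Appendix 7, Table 5, gives two marked low grades for fibrinogen:

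- LL, the milder: "< 0.75 - 0.5 LLN or 25 - < 50% decrease from baseline"
- LLL, the graver: "< 0.25 LLN or < 75% decrease from baseline or absolute value < 50 mg/dL"

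SAP Section 15.2.1, Table 16, carries the same low-side criteria, with LLL as "< 0.25 LLN or < 75% decrease from baseline or absolute value < 0.5" in g/L. The unit was converted (50 mg/dL is 0.5 g/L) and a high threshold of 6.0 was added where the protocol defines none. The percentage clause was left as it was.

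Appendix 7 says that one purpose of the thresholds is to flag or "communicate abnormal laboratory results from the central laboratory to the investigators"; another is standardized analysis by the sponsor. It also says "Laboratory values below or above the normal range will be graded at three levels", and "Thresholds for abnormality of level L or H are not provided in this appendix but will be provided in the laboratory manual". SAP Section 11.2.15 defines a reference-range indicator that "is derived to identify marked abnormalities according the Adapted table 5 from the study protocol". The indicator starts from the laboratory's own range flag, which the table then supplements or changes.

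Protocol Section 7.6 gives the sampling schedule: "IgM, IgG, IgA, CRP, fibrinogen, and BLYS (Visit 2 and Visits 4 to 7". That is one baseline and four later samples.

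**The concern.** A graver grade should need a larger fall than a milder one. Here LL needs a fall of at least 25%, while LLL is met by any fall short of 75%. The two percentage clauses overlap where they should be separate, and the largest falls drop out of the graver one. The level clauses have a separate fault: LL stops at 0.5 LLN and LLL begins below 0.25 LLN, with nothing assigned between.

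A programmer or laboratory that applies the row literally would rank trivial falls above grave ones. Because the SAP counts the worst abnormality per subject in each direction, one small fall at one visit would be enough to place a subject in the LLL column.

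**Working it through.** **Inputs.** LLN 2.1 g/L and ULN 4.7 g/L (SAP Section 5.7.3.2, Table 5, and Table 16). LL by level: 0.5 to 0.75 LLN. LLL by level: below 0.25 LLN or below 0.5 g/L. Fall clauses as quoted. One baseline and four post-baseline samples. The documents state no expected rate of LLL, so there is no plan figure to reproduce.

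**Step 1: level bands.** LL: 0.5 × 2.1 = 1.05 to 0.75 × 2.1 = 1.575 g/L. LLL: below 0.25 × 2.1 = 0.525 g/L. Values from 0.525 to 1.05 g/L are in neither marked grade by level. They are below LLN, so they still count as L, which is milder than the grade given to a less abnormal value of, say, 1.2 g/L. The absolute clause (below 0.5 g/L) does not close the gap.

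**Step 2: direction.** Fall = (baseline − value) / baseline.

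| Baseline → value (g/L) | Fall | Value / LLN | Marked grade met as written |
|---|---|---|---|
| 3.4 → 3.3 | 2.9% | 1.57 | LLL (fall) |
| 2.2 → 2.0 | 9.1% | 0.95 | LLL (fall) |
| 3.4 → 2.4 | 29.4% | 1.14 | LL and LLL (fall) |
| 3.4 → 0.9 | 73.5% | 0.43 | LLL (fall) |
| 3.4 → 0.8 | 76.5% | 0.38 | none |
| 4.0 → 0.6 | 85.0% | 0.29 | none |
| 3.4 → 0.51 | 85.0% | 0.24 | LLL (level) |

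The second and fifth rows show that the order is still reversed when only values below LLN are graded: 2.2 to 2.0 g/L is LLL, and 3.4 to 0.8 g/L has no marked grade.

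**Step 3: share graded LLL with no true change, if falls within the normal range count.** With exchangeable continuous values, a subject escapes only if baseline is the lowest of k + 1 values, so P(at least one fall) = k / (k + 1):

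- one visit: 1/2 = 50%
- three on-treatment visits: 3/4 = 75%
- four visits to end of study: 4/5 = 80%

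**Step 4: simulation check.** 200,000 subjects per setting. Assumptions not in the documents: mean 3.4 g/L (the midpoint of the reference range), between-subject SD 0.55 or 0.66 g/L, within-subject CV 5% to 20%, values unrounded or rounded to 0.01 or 0.1 g/L.

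- Four visits, falls within range graded: about 72% to 80%. The lower figures come from rounding to 0.1 g/L, where ties with baseline are not falls.
- Four visits, only values below LLN graded: about 1% to 13%.
- Percentage clause reversed to a fall of 75% or more: at most 0.001% in every setting.

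**The case against.** A reader might infer that about 80% of subjects in every arm will be reported as LLL, that a real fall in fibrinogen would be hidden, and that sites will receive a stream of false flags. The documents do not support that stronger reading, for these reasons.

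- Appendix 7 can be read to grade only values outside the normal range, and then an in-range fall earns no low grade. The contrary reading is also open: Table 5 restricts baseline clauses explicitly for hemoglobin and INR but not for fibrinogen, and the SAP lets the table change the laboratory's flag. The text does not settle it.
- The 80% also needs four visits. SAP Section 10.9 uses safety data to end of study, but Section 10.9.4 summarizes over the treatment period, which gives three visits.
- It is unclear whether the SAP grades fibrinogen at all. Section 11.2.15 leaves biomarkers out of the safety laboratory dataset, Section 5.7.3.2 lists fibrinogen as an exploratory biomarker, and the coagulation panels in both documents omit it. Table 16 nevertheless lists it under coagulation.
- A real fall would still show. SAP Sections 5.7.3.2 and 10.8.1.2 summarize the biomarkers by visit and arm, as values and changes or in categories, and the low fibrinogen categories there have no such gap (below 0.5, 0.5-1.0, 1.1-2.0 g/L).
- SAP Section 11.2.15 describes the laboratory's indicator as L, LL, H and HH, without LLL, and the laboratory manual is not available here. What sites would receive is therefore not known. Fibrinogen carries no alert in Table 5.

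These points limit the consequence. None of them repairs the row, which reverses the order of severity on either reading.

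**Conclusion.** The point holds as a defect in the grading row of both documents. The LLL percentage clause is inverted relative to LL, and 0.25-0.5 LLN falls outside both marked grades by level while remaining L. This rests only on the text and the LLN of 2.1 g/L.

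The size is conditional. If in-range falls are graded, about 72-80% of subjects with no true change would be LLL at least once to end of study, 75% over three on-treatment visits with unrounded values, and 50% at a single visit. If only values below LLN are graded, it is about 1-13% under the assumed distributions. An unconditional 80% is not supported.

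The effect is confined to laboratory flags and marked-abnormality tables. The main pharmacodynamic endpoint is untouched. It is a correction that should be made, of limited reach.

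**What to change.** In Protocol Table 5, SAP Table 16 and the laboratory flag specification:

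1. Reverse the LLL percentage clause so that it captures falls of 75% or more.
2. Make LL and LLL contiguous. Two bands need an owner: 0.25-0.5 LLN by level, and the 50-75% fall that step 1 would leave ungraded. The documents do not say which grade these belong to, so take the assignment from the grading system that Appendix 7 names as its main source (CTCAE 2010 v4.03).
3. State whether a value must be below LLN before a fall from baseline can earn a low grade.
4. Reconcile SAP Section 11.2.15, which excludes biomarkers, with Table 16, which lists fibrinogen under coagulation, so that it is clear whether the grade is derived and tabulated.

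The cost is one row in each table, one line in the laboratory specification and one sentence in SAP Section 11.2.15. No new data are needed.

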**Appendix 8 Corticosteroid conversion table**

Corticosteroid Conversion Table		
Glucocorticoid	Approximate equivalent dose (mg)	Half--life (hr)
Short-Acting		
Cortisone	25	8-12
Hydrocortisone	20	8-12
Intermediate-Acting		
Methylprednisolone	4	18-36
Prednisolone	5	18-36
Prednisone	5	18-36
Triamcinolone	4	18-36
Long-Acting		
Betamethasone	0.6-0.75	36-54
Dexamethasone	0.75	36-54

1. Dixon JS. Second-line Agents in the Treatment of Rheumatic Diseases. Informa Health Care, 1991. (456).
  2. Meikle AW and Tyler FH. Potency and duration of action of glucocorticoids. Am J of Med 1977;63;200.
- Source: [http://med.umkc.edu/docs/em/Corticosteroid\\_Table.pdf](http://med.umkc.edu/docs/em/Corticosteroid_Table.pdf)

---

**Appendix 9      Physician's Global Assessment Visual Analog Scale**

[figure not shown]

[figure not shown]
From: [Petri 2005](#)

**Appendix 10 SF-36v2™**

**United States (English) SF-36v2 Standard**

**Confidential**

## **LIST OF ABBREVIATIONS AND ACRONYMS**

|              |   |
|--------------|---|
| ACR          | American College of Rheumatology                                |
| AE           | Adverse event   |
| AESI         | Adverse event of special interest                               |
| ALT          | Alanine aminotransferase  |
| ALP          | Alkaline Phosphatase  |
| ANA          | Anti-nuclear antibodies   |
| ANCOVA       | Analysis of covariance  |
| anti-dsDNA   | Anti-double-stranded deoxyribonucleic acid                      |
| APL          | Immunoglobulin A Phospholipid                                   |
| AST          | Aspartate aminotransferase                                      |
| ATC          | Anatomic therapeutic chemical                                   |
| BLyS         | B-lymphocyte stimulator   |
| BP           | Blood pressure  |
| bpm          | Beats Per Minute  |
| CCM          | Central Clinical Monitoring                                     |
| CI           | Confidence interval   |
| CRP          | C-reactive protein  |
| CL           | Confidence limit(s)   |
| CSR          | Clinical study report   |
| CTCAE        | Common Terminology Criteria for Adverse Events                  |
| $C_{trough}$ | Measured plasma concentration at the end of one dosing interval |
| CXCL10       | C-X-C motif chemokine 10  |
| DBP          | Diastolic blood pressure  |
| ECG          | Electrocardiogram   |
| eCRF         | Electronic case report form                                     |
| EDTA         | Ethylenediaminetetraacetic acid                                 |
| $E_{max}$    | Maximum effect  |

|                  |  |
|------------------|--|
| EOS              | End-of-study                                 |
| EOT              | End-of-treatment                             |
| FAS              | Full analysis set                            |
| FDA              | (US) Food and Drug Administration            |
| FEV 1 | Forced expiratory volume in 1 second         |
| FSFV             | First subject first visit                    |
| FU               | Follow-up                                    |
| FVC              | Forced vital capacity                        |
| GPL              | Immunoglobulin G Phospholipid                |
| HIV              | Human immunodeficiency virus                 |
| HR               | Heart rate                                   |
| ICH              | International Council for Harmonisation      |
| IDMC             | Independent Data Monitoring Committee        |
| IgA              | Immunoglobulin A                             |
| IgG              | Immunoglobulin G                             |
| IgM              | Immunoglobulin M                             |
| INR              | International Normalized Ratio               |
| IR               | Interim safety review                        |
| IRT              | Interactive response technology              |
| LLN              | Lower limit of the normal ranges             |
| LLOQ             | Lower limit of quantification                |
| MCH              | Mean corpuscular hemoglobin                  |
| MCHC             | Mean corpuscular hemoglobin concentration    |
| MCP              | multiple comparison procedures               |
| MCV              | Mean corpuscular volume                      |
| MedDRA           | Medical Dictionary for Regulatory Activities |
| MPL              | Immunoglobulin M Phospholipid                |
| LSLV             | Last subject last visit                      |
| NA               | Not applicable                               |

---

[figure not shown]
|           |   |
|-----------|---|
| OCT       | Optical coherence tomography                                    |
| PD        | Pharmacodynamic   |
| PGA       | Physician's Global Assessment                                   |
| PK        | Pharmacokinetic   |
| PPS       | Per-protocol analysis set                                       |
| QTcB      | QT corrected for heart rate on the basis of Bazett's formula    |
| QTcf      | QT interval corrected for heart rate using Fridericia's formula |
| S1P       | Sphingosine-1-phosphate   |
| S1P1      | Sphingosine-1-phosphate receptor 1                              |
| SAE       | Serious adverse event   |
| SAF       | Safety analysis set   |
| SAP       | Statistical analysis plan                                       |
| SAS       | Statistical analysis system                                     |
| SBP       | Systolic blood pressure   |
| SF-36v2   | 36-Item Short Form Health Survey v2                             |
| SLE       | Systemic lupus erythematosus                                    |
| SLEDAI-2K | Systemic Lupus Erythematosus Disease Activity Index-2000        |
| SOC       | System organ class  |
| SDTM      | Study Data Tabulation Model                                     |
| SI        | Standard International  |
| TEAE      | Treatment-emergent adverse event                                |
| TB        | Tuberculosis  |
| TBL       | Total bilirubin   |
| ULN       | Upper limit of the normal ranges                                |
| ULQ       | Upper limit of quantification                                   |
| VPCs      | Ventricular premature complexes                                 |
| WBC       | White blood cells   |
| WHO       | World Health Organization                                       |
| WOCBP     | Women of childbearing potential                                 |

